11.2 Additional (Non-Primary) Efficacy Analyses

Models as detailed in equations (1) to (3) above an analogous approach will be used to assess 365-day differences with other corrections described next. Estimates from these models will account for design aspects such as potential within-site clustering that might otherwise lead to biased estimates in the standard errors associated with the regression coefficients. Additionally, we will control for clinically important variables, including pre-randomization ICH volume, IVH volume (or presence, depending on the variability in IVH volumes), baseline stroke severity, age, co-morbidity (diagnosis of diabetes or history of cardiovascular disease), and extent of white matter disease.

11.2.1. Additional Efficacy Analysis: Ordinal, Adjudicated mRS (0-6) at 365 Days

When we consider analysis of the ordinal mRS, we will estimate a proportional odds model of the form:

 $\log \frac{\gamma_k}{1-\gamma_k} = \alpha_k + \beta X + \theta Trt$ (6)

where α_k = Prob(mRS < k), *k*=0, 1,...,5.

This proportional odds model is very similar to the models described under 11.1. above, with the difference being that a treatment effect leads to an increase in the likelihood of a patient being in any subsequently lower mRS category. The probabilities, α_k , are cumulative probabilities which incorporate all outcomes below any given level. The set of intercepts, $\alpha_k = 0, 1, ..., 5$, define the initial probabilities of these cumulative levels, covariates are again included through β and X, and the treatment difference θ now describes the log-odds of moving from any cumulatively higher (worse) category, into any cumulatively lower (better) category. For instance, here θ describes both how the MIS+rt-PA changes the probability of ICH patients away from a potential mRS category of "Dead" (6) to "No Symptoms through Severe Disability" (0-5), as well as how the MIS+rt-PA changes patient probabilities away from "Severe Disability or Dead" (5,6) to "No Symptoms through Moderate Disability" (0-4) and so forth. This model is potentially more efficient than a simple dichotomous approach since it uses the available information across the scale of the measure. To examine the proportional odds assumption, we will additionally examine generalized ordered logit models that replace β and θ with β_k and θ_k , allowing non-parallel effects between successive cumulative categories. In the event that the proportional odds assumption is rejected, we will present results from the generalized ordered logit models.

For the ordinal outcome, the average treatment effect is defined as the average of the cumulative logodds:

$$\beta = \frac{1}{K-1} \sum_{i=1}^{K-1} \log \frac{\frac{P(Y_1 \le i)}{P(Y_0 \le i)}}{\frac{P(Y_0 \le i)}{P(Y_0 \ge i)}} \quad (7)$$

where Y_r is the mRS score at 365 days and r=1 for MIS+rt-PA and 0 for medical management.

Survival models will be constructed to examine the mortality for the MIS+rt-PA and medically managed groups. Standard Cox proportional hazard models will initially be examined. These models are commonly written as:

$$h_i(t) = \lambda_0(t) \exp(\gamma X + \phi \cdot TRT)$$
 (8)

where $\lambda_0(t)$ is a non-parametric baseline hazard function, γ is a vector of regression coefficients related to the X covariates, and ϕ is the parameter for the treatment effect of MIS+rt-PA on the hazard of death (mortality). This model may be extended by including time-dependent covariates and non-proportional hazards as deemed necessary through diagnostic checks. Observed mortality will also be compared with predicted mortality based on clinical presentation, overall, and by treatment group. Predicted mortality will be estimated. We will develop a severity model that predicts mortality based on the Tuhrim model.^{2,7,8}

11.2.2. Additional Efficacy Analysis: Longitudinal Analysis

Longitudinal analysis will examine the secondary outcomes that are longitudinally collected at baseline and the follow-up time points (e.g., at 30, 90, 180, 270, and 365 days post-stroke). These data will have within-patient correlations from one time point to the next, making it necessary to use appropriate analytical methods that properly estimate the coefficients and their associated standard errors in the analysis models. Since the overall goal of the trial is to compare subjects receiving the MIS+rt-PA intervention with subjects receiving medical standard of care, a marginal model estimated using a generalized estimating equations (GEE) technique is appropriate. The GEE technique requires specification of the standard "mean" model, as well as specification of a working "association" model. One strength of GEE is that the fixed-effect parameters in the mean model (i.e., the intervention effect) are consistent regardless of whether the association model is specified correctly under mild regularity conditions. The fixed-effects will include treatment arm (coded as 1 for MIS+rt-PA and 0 for medical management), follow-up time represented with four indicator variables for 90, 180, 270, and 365 days post ictus), and their interactions. The interaction terms will test (at 0.05 level of statistical significance) whether the longitudinal change in the outcome is statistically different between study arms. Additional variables will include ICH volume, baseline GCS, age, IVH, and comorbidities, such as history of diabetes or cardiovascular disease. Models will be compared using guasi-likelihood under the independence model criterion (QIC) for GEE.

11.2.3. Additional Efficacy Analysis: Severity Subgroup Analysis

Regression of the treatment by subject severity. In subsequent analyses, the model in equation (1) will be modified to include multiple baseline severity variables, such as NIHSS, IVH, extent of white matter disease, co-morbidity, etc. The models will be compared using Akaike Information Criterion (AIC) to assess the best combination of predictors. The discriminatory ability of the models will be compared using the cross-validated area under the Receiver Operating Characteristic (ROC) curve.

11.2.4. Additional Efficacy Analysis: Subgroup Analysis

Summary statistics will be presented for the analysis sets and subgroups of gender, race, and ethnicity. In addition, summary statistics will be examined for the subgroups of the patients who completed the study and by patients who discontinued the study early from the data available for these patients. The reasons for early discontinuation, including bleeding, loss to follow-up, and withdrawal of care, will be tabulated and recorded to help improve future recruitment and retention.

In addition, since data from the MISTIE phase 2 trial neither supports nor negates any significant difference in treatment efficacy by gender, race, or ethnicity, the analyses detailed in equations (1) to (4) above will be performed separately for males and females, by race (e.g., Caucasian, African

American, Asian, Native American, Pacific Islanders, etc.), and by ethnicity (e.g., Hispanic, non-Hispanic), where adequate data are available to determine if the treatment effect varies by these demographic categories, which would indicate the presence of effect modification by treatment. These sub-analyses are required by the NIH Policy and Guidelines on The Inclusion of Women and Minorities as Subjects in Clinical Research, amended October 2001. Note that the trial is not powered to see treatment effect modifications by these demographic categories.

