The above stopping boundaries are used after 250, 375 and 500 patients, respectively, have 180-day post-stroke measurements. If the test statistic described above exceeds the efficacy boundary, or if it is less than the futility boundary, the enrollment of patients is stopped early. The futility boundary at each interim analysis corresponds to a one-sided test at level 0.0001 of the hypothesis that the probability of a “good” outcome (mRS 0-3) is  $\geq 11\%$  under assignment to MIS+rt-PA vs medical management. These boundaries are more aggressive than the efficacy boundaries (the latter of which are based on O'Brien-Fleming boundaries, but are proportionally increased to strongly control the study-wide Type I error rate at the 5% level).

The above design has the following properties as described in Figure 1 and Table 2:

- i) At least 88% power to detect a treatment benefit  $\geq 13\%$ , assuming the probability of mRS 0-3 under medical management is 25%;

- ii) At least 81% power to detect a treatment benefit  $\geq 11\%$ , assuming the probability of mRS 0-3 under medical management is 20%.

**Table 2. Estimated Power for Risk-Difference Effect Sizesa from 10-13% (N=500) by Probability of mRS 0-3 in Medical Management Arm**

	Base Plan b	Plan B b
Effect Size	Probability = 0.25	Probability = 0.20
13%	88%	91%
12%	83%	87%
11%	76%	81%
10%	68%	73%

a MIS+rt-PA – medical management

b Tables 4, 5 in CCC grant

[figure not shown]

Figure 1. Power curves at ranges of effect sizes on risk difference scale, assuming baseline probability of modified Rankin Score 0-3 for medically-managed patients = 25%

**9.1.10. Statistical Power for Secondary Aim 2a.** Based on MISTIE II data (Table 1), the relationship between mRS score and EOT clot size is estimated as an OR (95% CI) of 3.82 (0.97-15.1,  $p=0.056$ ). Simulations were performed on 1000 generated samples of 250 patients per group based on randomized MISTIE II patient data. These simulations indicate that with 500 total patients the estimated power to detect an adjusted OR of 3.82 is  $\geq 98\%$ . Additional simulations suggest that there is  $\geq 90\%$  power for detecting an adjusted OR as low as 2.38 to evaluate the strength of the relationship between clot size, dichotomized as  $\leq 15$  vs  $> 15$  mL and mRS outcome (0-3 vs 4-6).

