2.0. Objectives of the Study

2.1. Efficacy

The primary aim of this multicenter, international, randomized, open-label, phase 3 trial is to determine the efficacy of intra-clot catheter placement and aspiration of hematoma contents, followed by gentle clot irrigation with low dose recombinant tissue plasminogen activator (rt-PA), referred to as Minimally Invasive Surgery plus rt-PA (MIS+rt-PA). The primary hypothesis of this trial is that the MIS+rt-PA approach to intracerebral hemorrhage (ICH) management will result in more patients having overall better functional outcome at 365 days, as defined by the proportion of subjects with dichotomized, adjudicated modified Rankin Scale (mRS) score 0-3 vs. 4-6, when compared to the mRS scores for patients managed with standard aggressive medical treatment. Although the mRS includes a category for death, and hence the primary analysis incorporates mortality outcomes, in-hospital and 30-day mortality will also be examined as safety outcomes for the trial. Furthermore, 365-day mortality will be evaluated separately as a secondary efficacy outcome. An intent-to-treat (ITT) paradigm for the analyses will be incorporated. The MISTIE III trial will enroll a total of 500 eligible patients, 250 randomized each treatment arm (MIS+rt-PA or medical management). The power to detect (88%) is for an estimated effect size of 13% across all clot locations with this sample size (500).

Additional analyses of efficacy outcomes will evaluate the therapeutic benefit of MIS+rt-PA relevant to medical management in improving subjects' function and quality of life at 365 days post symptom onset as measured by extended Glasgow Outcome Scale (eGOS), days in various locations such as home

Minimally Invasive Surgery Plus rt-PA for ICH Evacuation Phase 3

during the 365-day period, patient disposition at 180 and 365 days including proportion of days in longterm care facilities, National Institutes of Health Stroke Scale (NIHSS), Barthel score, days in hospital, days in intensive care unit (ICU), Stroke Impact Scale (SIS), Preference-Based Stroke Index (PBSI), EuroQol-5 Dimension (EQ-5D), Mini-Mental State Examination (MMSE), Personal Health Utility Interview, and Center for Epidemiological Studies – Depression (CES-D).

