5.5. Demographic and Clinically Specific Subgroups

All the primary, secondary, and safety analyses will be performed by gender, race, and ethnicity to determine if the treatment effect or safety differs by these demographics. Patient-specific clinical or "severity" factors/categories and treatment categories will be explored. Planned explorations include age, GCS (or NIHSS), ICH location, time to treatment, and initial ICH size.

Subgroups utilized for adaptive cut points are: age <56, age 56 through 67, and age \geq 67; GCS 3–8, 9– 12 and 13–15; initial ICH size (0–<25; 25–<35; 35–<45; 45–<55; 55–<65; and \geq 65). We will examine the following subgroups: stability ICH size <50 and \geq 50; lobar vs. deep; stability IVH size; time to surgery at <24 hours, 24-48 hours, and >48 hours from ictus; GCS 3–8, 9–12 and 13–15; and age <65 and \geq 65.

Additional analysis of groupings of these clinical factors will be dictated by group size and balance between groups. We will also explore time as a continuum and at other clinically meaningful cut points. We will treat age, ICH size, and IVH size as a continuum and collapse them to other meaningful subgroups, as described above. NIHSS and GCS will also be treated as a continuum of scores. Based on post hoc analysis of the STICH trials, we will evaluate GCS 9–12 versus all other score levels.

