8.0. Multiplicity

The primary analysis of efficacy is tested at the two-sided alpha level of 0.05. In addition, secondary analyses will consider the alpha=0.05 two-sided type I error. Secondary analyses will be examined in the order specified and will not be corrected for multiplicity of testing.

Secondaries 2-7 are defined. The other analyses without specific hypotheses are considered exploratory. We will present descriptive statistics and CIs.

For safety outcomes, we do not account for multiplicity as this study was not powered to observe safety. Thus, a cautionary approach is justified.

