Methods of non-inferiority will be used to statistically determine if the proportions of a particular type of SAE, where there are adequate data for a particular type, are not substantially different among both treatment groups in order to test the hypothesis that MIS+rt-PA is as safe as standard medical management. Non-inferiority testing deems the rates of any SAE event in the MIS+rt-PA group to not be substantially greater than the SAE event rate in the standard medical management group as long as the group difference in this rate is statistically within some pre-specified tolerance. For this trial, the tolerance value will be defined as 10% for the primary adverse events of 30-day mortality, rebleeding, and infection, and 5% for first-week operative mortality. Thus, the rates of adverse events seen in the MIS group can be higher than those in the medically managed group, and yet still be considered not substantially different as long as the upper one-sided 95% CIs on rate differences are $\leq 10\%$ or $\leq 5\%$, depending on the safety measure.

Minimally Invasive Surgery Plus rt-PA for ICH Evacuation Phase 3

Since data from the MISTIE phase 2 trial neither supports nor negates any significant difference in SAE event rates by gender, race, or ethnicity, the non-inferiority analyses described above will be performed separately for subpopulations within each of these demographics where there are adequate data available.

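### The SAP aims to detect effect modification by gender, race and ethnicity from separate within-group analyses, and specifies no between-group contrast

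*SAP*

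**What the plan says.** SAP 11.2.4 runs the primary-type models separately for males and females, by race and by ethnicity, where data are adequate. The stated purpose is "to determine if the treatment effect varies by these demographic categories, which would indicate the presence of effect modification by treatment". The section adds that the trial is not powered for such effect modification and that NIH policy requires the sub-analyses.

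SAP 5.5 is broader: "All the primary, secondary, and safety analyses will be performed by gender, race, and ethnicity to determine if the treatment effect or safety differs". In SAP 14.1, "the non-inferiority analyses described above will be performed separately for subpopulations" defined by gender, race and ethnicity, again where data are adequate.

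Each repeat of the SAP 11.1 analysis brings its own decision rule: reject the null if the 95% bootstrap confidence interval excludes zero. No section says how results in one group are to be compared with those in another.

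Interactions are specified for other questions:
- treatment by time (SAP 11.2.2)
- missing-visit indicators by arm (SAP 11.1)
- clot-reduction category by treatment (Protocol 9.1.7, Analysis 2b)
- treatment by spot sign and by microbleeds (Protocol Appendix 8, section 7)

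None is specified for sex, race or ethnicity. SAP 2.2 lists the demographic mRS analysis as exploratory, and SAP 8.0 promises descriptive statistics and CIs for analyses without specific hypotheses.

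**The concern.** Whether an effect differs between two groups is a question about the difference between two estimates. An analysis inside one group asks only whether that group's effect differs from zero. Each group has fewer patients than the trial, so each has limited power. A uniform effect can easily reach significance in one group and miss it in the other.

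The plan states the between-group question but specifies only the within-group analyses. A reader of the results could conclude that the treatment works, or is acceptably safe, in one sex or race and not in another when nothing differs. The power caveat in 11.2.4 warns of missing a real difference. It does not warn of an apparent difference produced by low power within groups.

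**Working it through.** **Inputs from the documents.** SAP 2.1: 500 patients, "250 randomized each treatment arm (MIS+rt-PA or medical management"). SAP 8.0: "The primary analysis of efficacy is tested at the two-sided alpha level of 0.05". Protocol 9.1.9: a 13-point effect "assuming the probability of mRS 0-3 under medical management is 25" per cent, and an 11-point effect "assuming the probability of mRS 0-3 under medical management is 20" per cent. SAP 4.0: a 16.2-point adjusted phase 2 estimate, used for sensitivity.

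**Assumptions.** Group shares are not in the documents. Each group is taken to split equally between arms. The calculation is unadjusted and uses the 180-day planning rates.

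**Step 1: reproduce the plan's power.** With n per arm, power = Φ[(d − 1.96·s0)/s1], where s0 = √[2·p̄(1−p̄)/n] and s1 = √[p1(1−p1)/n + p2(1−p2)/n]. The opposite tail is negligible at these effect sizes; it is included for the small effects in step 4.
- 25% vs 38%, n = 250: s0 = 0.04155, s1 = 0.04114, (0.13 − 0.08143)/0.04114 = 1.18, power 88.1% (stated 88%).
- 20% vs 31%, n = 250: s0 = 0.03899, s1 = 0.03867, (0.11 − 0.07641)/0.03867 = 0.87, power 80.7% (stated 81%).

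**Step 2: power within a group.** At a 50/50 split, n = 125 per arm. For 25% vs 38%, s0 = 0.05876, s1 = 0.05818, and (0.13 − 0.11516)/0.05818 = 0.255, giving 60.1%.

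**Step 3: chance of split verdicts under a uniform effect.** The groups share no patients, so with rejection probabilities a and b the chance that exactly one is significant is a(1−b) + b(1−a).

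| Group shares (assumed) | 25%, +13 points: a, b | Split verdict | 20%, +11 points: a, b | Split verdict |
|---|---|---|---|---|
| 50% and 50% | 0.601, 0.601 | 48% | 0.514, 0.514 | 50% |
| 60% and 40% | 0.680, 0.508 | 50% | 0.590, 0.430 | 51% |
| 70% and 20% | 0.747, 0.286 | 61% | 0.657, 0.241 | 58% |

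Worked case, last row: 0.747 × 0.714 + 0.286 × 0.253 = 0.61. Simulation of 200,000 trials agreed within 1 point for the two-way splits run (50/50 to 80/20).

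**Step 4: sensitivity to the uniform effect (50/50, control 25%).**
- 16.2 points: a = b = 0.780, split 34%
- 10 points: 0.407, split 48%
- 5 points: 0.143, split 25%
- zero: 0.05, split 9.5%

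**Step 5: a direct test of the difference.** Let D be the difference between the two groups' risk differences, with SE = √(SE_A² + SE_B²).
- False positives under the same uniform effects: 5.1–5.4% in simulation.
- Power at 50/50: SE = √[2 × (0.1875 + 0.2356)/125] = 0.0823. A 13-point difference in effect gives 0.13/0.0823 − 1.96 = −0.38, or 35% power. For 80% power the difference must be (1.96 + 0.84) × 0.0823 ≈ 23 points.

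**Step 6: safety illustration.** SAP 14.1 uses a 10-point margin and an upper one-sided 95% bound. Assume identical true 30-day mortality in both arms, at 10% or 15% (the phase 2 arm rates in Protocol 2.2). The chance of showing non-inferiority is Φ[0.10/√(2p(1−p)/n) − 1.645]. For two equal groups (n = 125 per arm) this is 0.84 or 0.72, so the verdicts split 27% or 41% of the time.

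**The case against.** The strongest reply is that the plan never prescribes comparing significance between groups. SAP 11.2.4 gives no comparison rule, the repeated analysis yields an estimate with a 95% CI, and SAP 8.0 presents exploratory analyses descriptively. This stands. The percentages in step 3 are the error rate of a reading the plan leaves open, not of a procedure it specifies. A reader might infer that the SAP has adopted a rule that is wrong half the time; the documents do not support that.

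A reader might also infer that the planned method cannot serve its purpose at all. That is too strong. The groups are disjoint, so the planned stratum-specific estimates already contain what is needed to form the contrast. What is missing is a statement that it will be formed and used.

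Three further points stand in part:
- The size depends on the true effect and on assumed shares, and the primary endpoint is now at 365 days with covariate adjustment. The figures are therefore conditional and shown as a range.
- SAP 14.1 does not itself state an aim of detecting effect modification. For safety, that aim comes from SAP 5.5.
- An interaction test would miss most moderate differences. This limits what can be learned about subgroups, but it does not make separate verdicts a valid substitute.

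**Conclusion.** The point holds in a limited, conditional form. SAP 11.2.4 and 5.5 state a between-group aim, specify only within-group analyses, and leave the comparison undefined.

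If verdicts are compared on significance, a uniform effect of the planned size produces a split result about 48–51% of the time for two groups between 50/50 and 60/40, and about 58–61% for groups of 70% and 20%. This is not a general figure: step 4 shows how far it falls when the uniform effect is larger or smaller than planned. All of it rests on assumed shares.

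It would be wrong to infer that the trial's main result is at risk. The subgroup analyses are exploratory, and the primary estimate, its error rate and the trial's conclusion do not depend on them. The change is worth making because it is cheap and prevents a foreseeable misreading.

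**What to change.** In SAP 11.2.4 and 5.5, and for the safety rate differences in 14.1, state that effect modification by gender, race and ethnicity is judged by the difference in risk differences between groups, with its 95% CI and an interaction p-value. Use a multi-degree-of-freedom test for race. State that within-group estimates and CIs are descriptive and are not compared on significance.

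The contrast can be computed from the stratum-specific estimates or from the bootstrap already planned in SAP 11.1. Adding one product term to a model would not be enough. The primary estimator is a sequence of weighted logistic fits, a product term there gives an interaction on the logit scale, and race has several categories.

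The cost is a few sentences and some extra analysis, with no new data. The limits should be written in: power is low (step 5), and nothing corrects for testing three factors, where at least one false positive would arise about 1 − 0.95³ = 14% of the time if the tests were independent. The tests should be labelled exploratory.
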